3. STUDY DESIGN

This is a Phase 3b/4, multicenter, randomized, assessor blinded, vehicle and active (TCS and TCI) controlled study of the efficacy, safety and local tolerability of crisaborole ointment, 2% in pediatric and adult subjects, ages 2 years and older, with mild to moderate AD involving at least 5% treatable %BSA. Treatment will be clinical assessor-blinded for all treatment arms and double-blinded for crisaborole ointment, 2% and vehicle treatment arms.

A total of approximately 600 subjects will be enrolled in the study, of which at least 150 subjects aged 2-6; at least 140 subjects aged 7-11; at least 120 subjects aged 12-17 and up to 90 subjects will be adults. Following the screening period (up to 35 days prior to Baseline/Day 1), eligible subjects will be randomized at the Baseline/Day 1 visit.

Randomization will be stratified by eligibility for TCS or TCI treatment as per national approved labels and eligibility provided in [Section 4](#). Cohort 1 will be for subjects who are eligible for TCS therapy, and Cohort 2 will be for subjects who are not eligible for TCS therapy but eligible for TCI therapy. The investigational product will be applied BID for 28 days to the Treatable BSA identified at Baseline/Day 1. Any new AD on treatment-eligible locations occurring following Baseline/Day 1 should also be treated with the study drug after consultation with the Investigator at the next visit.

The primary efficacy endpoint is the percent change from baseline in the EASI total score at Day 29.

For the efficacy comparison of crisaborole versus vehicle, subjects from both Cohort 1 and Cohort 2 are included in the analysis, adjusted for cohort effect. For the efficacy comparison of crisaborole versus TCS, only subjects from Cohort 1 are included in the analysis. For the comparison of crisaborole versus TCI, only subjects from Cohort 2 are included in the analysis.

[figure not shown]
Safety and efficacy assessments will be conducted at the investigator site by a clinical assessor blinded for treatment arms.

A sub-study will be conducted at selected investigator sites to evaluate differences of changes in epidermal skin thickness as measured by Optical Coherence Tomography (OCT) between treatment groups in Cohort 1. (see Appendix 4).

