Appendix 3. Very High/Very Strong and High/Strong Potency Topical Corticosteroids

Per [Exclusion Criterion 2](#). Based upon the World Health Organization classification where topical corticosteroids have been ranked in terms of potency into four groups consisting of seven classes.

Including but not limited to;

Very high potency topical corticosteroids

Group 1

- Clobetasol propionate cream (0.05%);
- Diflorasone diacetate ointment (0.05%).

High potency topical corticosteroids

Group II

- Amcinonide ointment (0.1%);
- Betamethasone dipropionate ointment (0.05%);
- Desoximetasone (cream or ointment) (0.025%);
- Fluocinonide (cream, ointment, or gel) (0.05%);
- Halcinonide cream (0.1%).

Group III

- Betamethasone dipropionate cream (0.05%);
- Betamethasone valerate ointment (0.1%);
- Diflorasone diacetate cream (0.05%);
- Triamcinolone acetonide ointment (0.1%).

Appendix 4. Optical Coherence Tomography Sub-Study – A Study of Optical Coherence Tomography and Biomarkers in Subjects ages 2 to <18 years old, with Mild to Moderate Atopic Dermatitis, treated with Crisaborole Ointment, 2% or Crisaborole Vehicle Ointment or Hydrocortisone Butyrate 0.1% Cream applied BID.

1. Introduction

Skin atrophy, characterized by whole skin thinning and damage to the skin barrier, is a common problem in the treatment of AD with TCS.¹ Often, effective treatment with TCS must be limited because of the risk of skin atrophy.¹ To further explore the benefit/risk of crisaborole ointment, 2%, this sub-study aims to evaluate differences in atrophic skin changes across study treatment groups in Cohort 1.

Optical coherence tomography (OCT) is a non-invasive imaging modality conceptually similar to ultrasound but uses near-infrared radiation rather than sound. It has a 2-10 micron depth resolution compared with 100-1,000 micron typical for clinical US; and 1-2 mm imaging depth vs. 10-100 mm for clinical US. It is thus ideal for imaging the surface layers of accessible tissues such as the skin.² OCT imaging will be obtained using the VivoSight OCT scanner, by Michelson Diagnostics, Ltd. in this sub-study to evaluate atrophic changes in epidermal thickness during and after treatment with study investigational product in Cohort 1.

This sub-study also provides an opportunity to explore differences in Transepidermal Water Loss (TEWL) and cutaneous inflammatory and barrier biomarkers associated with AD within the stratum corneum (SC) across treatment groups in Cohort 1.

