The Aquaflux device is an evaporimeter that measures water exchange through human skin using the condenser-chamber method. The condenser-chamber method uses a humidity gradient to determine the amount of water diffusing through the SC³. This device will be used in this sub-study to evaluate TEWL during and after treatment at select sub-study centers.

Tape-strips are a minimally invasive method that captures cutaneous inflammatory and barrier biomarkers within the SC, circumventing the need for skin biopsies, especially in the pediatric population. Studies have used proteomic immune assays and messenger ribonucleic acid analyses to evaluate SC biomarkers in tape-strips from AD lesional and non-lesional skin from patients with AD. Expression of AD-associated biomarkers in AD tape-striped skin have been significantly correlated with disease severity (EASI/pruritus) and the functional barrier measure TEWL. Tape-strips will be used in this sub-study to evaluate SC biomarkers from AD lesional and non-lesional skin.

2. Objectives and Endpoints

The primary objective of this sub-study is to evaluate the differences in atrophic changes in epidermal thickness by structural OCT after treatment with crisaborole ointment, 2% or

crisaborole vehicle ointment, or hydrocortisone butyrate 0.1% cream applied BID for 28 days.

The secondary objectives of this sub-study are to evaluate the differences in atrophic change in epidermal thickness, skin biomarkers of AD, and TEWL during the course of treatment and following treatment with crisaborole ointment, 2% or crisaborole vehicle ointment, or hydrocortisone butyrate 0.1% cream applied BID for 28 days.

This sub-study is expected to provide OCT, TEWL, and skin biomarker evidence of the effects of crisaborole ointment and vehicle ointment compared to TCS.

Primary Sub-Study Endpoint:

- Change in epidermal thickness from Baseline/Day 1 to Day 29

Secondary Sub-Study Endpoints:

- Change in epidermal thickness from Baseline/Day 1 to all sub-study time points except Day 29 (Days 8, 15, 22, and 60)
- Intrasubject difference of change in epidermal thickness between the non-lesional target skin site and the OCT AD lesional target skin site from baseline to Days 8, 15, 22, 29 and 60
- Percentage change from Baseline/Day 1 in TEWL at Days 8, 15, 22, 29 and 60
- Change from Baseline/Day 1 in skin biomarkers of AD at Day 15 and Day 29

3. Sub-Study Design

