Prior and concomitant topical treatments (per section 5.8) used on sub-study target skin sites will be recorded in the CRF. In addition to restrictions regarding concomitant medications described in section 5.8.4 of protocol, all effort should be made to not apply AD treatments to sub-study defined target skin sites after the treatment phase until the Day 60, End of Study Visit, even if other lesions are necessary to treat with concurrent treatment for AD.

7. Data Analysis/Statistical Methods

Approximately 60 subjects (15, 15, 30 in vehicle, crisaborole, hydrocortisone groups respectively) will participate this sub-study from Cohort 1. This sub-study is a pilot and there is no formal hypothesis testing. The sample size is not based on a power calculation and an estimation approach will be used for data analysis and interpretation.

The analysis of change from baseline to Day 8, Day 15, Day 22, Day 29, and Day 60 in epidermal skin thickness, will be analyzed using mixed model repeated measure (MMRM) with treatment, visit, treatment by visit interaction as factors and baseline value as a covariate, separately for OCT AD lesional target skin site and non-lesional target skin site. Within-subject variability will be accounted for using a random effect with the first order autoregressive (AR(1)) covariance matrix.

The same models as above will be used for percentage change from baseline in TEWL at Baseline/Day 1, Day 8, Day 15, Day 22, Day 29 and Day 60. No baseline value will be included as a covariate in the model.

Intra-subject difference of change from baseline to Day 8, Day 15, Day 22, Day 29, and Day 60 in epidermal skin thickness between OCT AD lesional target skin site and non-lesional target skin site will be analyzed using MMRM model with visit as a factor for each treatment group.

For the tape-strip biomarkers, Log2-scale quantitative reverse transcription polymerase chain reaction expression data will be modeled by a linear mixed effect model with visit, treatment, visit by treatment interaction as fixed effects and a random effect for each subject. Means of each group will be estimated using least squares means and comparisons of interest will be tested using contrast.

This sub-study will be reported independently from the main Clinical Study Report.

References

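### The sub-study's lesional versus non-lesional thickness endpoint has no planned between-arm estimate (minor; one secondary endpoint of a pilot)

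*Protocol*

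**What the plan says.** Appendix 4, section 2 of the protocol lists as a secondary sub-study endpoint the "Intrasubject difference of change in epidermal thickness between the non-lesional target skin site and the OCT AD lesional target skin site". It is assessed at five post-baseline visits, the last on Day 60. Section 7 of the appendix says that this endpoint "will be analyzed using MMRM model with visit as a factor for each treatment group". It names no treatment term, interaction or contrast for it.

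The other models in section 7 differ:
- Thickness change at each site, fitted separately for the lesional and the non-lesional site, uses a repeated-measures model "with treatment, visit, treatment by visit interaction as factors and baseline value as a covariate".
- Percentage change in TEWL uses the same model without the baseline covariate.
- The tape-strip biomarker model has visit, treatment and their interaction, and adds contrasts.

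The stated purpose is comparative throughout. In Appendix 4, section 1, "this sub-study aims to evaluate differences in atrophic skin changes across study treatment groups in Cohort 1". Protocol section 3 describes the sub-study as evaluating "differences of changes in epidermal skin thickness as measured by Optical Coherence Tomography (OCT) between treatment groups in Cohort 1". Appendix 4, section 2 expects "evidence of the effects of crisaborole ointment and vehicle ointment compared to TCS".

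Two further statements bear on interpretation. Appendix 4, section 6 has the non-lesional forearm site treated with investigational product for the whole 28-day period, like the lesional site. Section 7 says "This sub-study is a pilot and there is no formal hypothesis testing", and that the results will be handled by estimation.

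**The concern.** This is the only sub-study endpoint whose model has no treatment term, and no reason is given. On the plain reading, three separate fits produce three sets of within-arm means and no interval for the difference between any two arms.

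Within-arm results cannot stand in for that difference. Both sites in a subject receive the same product, so the lesional-minus-non-lesional value describes how diseased and clear skin differ under one product. Whether the products differ is a question about the contrast between randomised arms. If only within-arm results are tabulated, readers will tend to treat an interval that excludes zero in one arm and includes it in another as evidence that the arms differ. Unequal arm sizes make that more likely.

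**Working it through.** **Inputs.** Appendix 4, section 7: 15 vehicle, 15 crisaborole and 30 hydrocortisone butyrate subjects; five post-baseline visits. Protocol section 4.3: 1:1:2 allocation in Cohort 1. The documents give no SD for this endpoint, so widths below are in units of its SD at one visit, assumed common to the arms, with complete data.

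**The plan's own figure.** 60 × (1/4, 1/4, 2/4) = 15, 15, 30. This reproduces. The plan states no power or precision for the sub-study.

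**What each model estimates.**
- As planned: 5 visit means in each of 3 arms, 3 × 5 = 15 parameters, none of them a between-arm parameter.
- One joint model with treatment, visit and treatment by visit: 5 visit means in a reference arm plus 2 arm contrasts × 5 visits = 10, again 15 mean parameters, of which 10 carry the between-arm comparison.

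The two models describe the same 15 cell means. What is missing from the plan is the contrast and its interval.

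**Whether the site-specific models fill the gap.** They give arm differences at each site. They are fitted separately by site, so they do not supply a standard error for an arm difference in the lesional-minus-non-lesional quantity. That needs the within-subject covariance between sites: Var(L − N) = Var(L) + Var(N) − 2 Cov(L, N).

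**Precision of the between-arm estimate.** Half-width = t(0.975, df) × √(1/n1 + 1/n2), with df = 60 − 3 = 57 and t = 2.002.

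| Contrast | √(1/n1 + 1/n2) | Half-width |
|---|---|---|
| Crisaborole v vehicle (15 v 15) | 0.365 | 0.73 SD |
| Crisaborole or vehicle v hydrocortisone butyrate (15 v 30) | 0.316 | 0.63 SD |

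With 1.96 in place of t, these are 0.72 and 0.62 SD.

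**Why side-by-side reading misleads.** Taking one visit alone, the within-arm half-width is 2.145/√15 = 0.55 SD with 15 subjects and 2.045/√30 = 0.37 SD with 30. Suppose the observed mean were the same, 0.45 SD, in the crisaborole and hydrocortisone butyrate arms (a hypothetical value). The hydrocortisone interval would run from 0.08 to 0.82 and exclude zero. The crisaborole interval would run from −0.10 to 1.00 and include it. The estimated difference between the arms would be 0, with a half-width of 0.63 SD.

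**The case against.** The strongest reply is that little is lost, and much of it stands.

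- **The aim is served elsewhere.** The primary sub-study endpoint, thickness change to Day 29, has between-arm estimates at both sites. This stands and confines the point to one secondary endpoint.
- **The contrast can be derived.** The arms are independent, so a difference and its standard error follow from the per-arm fits. True, but the protocol does not plan it.
- **A per-arm model suits the question.** How lesional and non-lesional skin differ under the same product is a reasonable within-arm question, and separate fits allow each arm its own covariance. That justifies reporting within-arm means. It does not meet the comparative aim.
- **It is a pilot without tests.** The plan promises estimation, and an arm difference with an interval is an estimate.
- **The wording is loose.** It could mean visit effects estimated by group within one model. Even so, no treatment contrast is named.
- **Details lie elsewhere.** SAP section 2.2 defers the sub-study analysis to a separate SAP, and Appendix 4, section 6 defers OCT endpoint analyses to study-specific documents. Either may specify the contrast; neither could be checked.

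Two stronger readings are tempting and not supported. A reader might infer that separate fits materially widen every arm's interval. At a single visit, t on 14 df against 57 df gives 2.145/2.002 = 1.07 for the 15-subject arms, but t on 29 df gives only 2.045/2.002 = 1.02 for the 30-subject arm. Both ratios treat each visit as a separate analysis, whereas a repeated-measures fit with a common variance over visits would narrow the gap. A reader might also infer that this is among the sub-study's most informative endpoints. Subtracting one treated site from another can cancel thinning common to both. For two changes of equal variance σ² and correlation ρ, the difference has variance 2σ²(1 − ρ), which is smaller than σ² only if ρ exceeds 0.5. The documents give no ρ.

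**Conclusion.** The point holds and is minor. As the protocol is written, this secondary endpoint has no planned between-arm estimate, which departs from the sub-study's comparative aim and from every neighbouring model. The documents do not support saying that the sub-study as a whole fails to compare treatments, or that the randomised comparison is irretrievably lost.

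The conclusion rests on reading the sentence in section 7 as separate fits by arm, and on the unseen sub-study SAP not already adding the contrast. The precision figures of 0.73 and 0.63 SD rest on complete data, 15/15/30 subjects and a common SD. SAP section 5.1 reports that the main study was terminated with 40% of planned enrolment and limits its analysis to description. The sub-study has its own SAP and is to be reported independently, so that decision does not by its text settle this model. Fewer subjects would give wider intervals than those shown.

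**What to change.** Replace the sentence in Appendix 4, section 7 with a single repeated-measures model for the intra-subject difference, with treatment, visit and treatment by visit as factors. Report between-arm differences with 95% confidence intervals at Days 8, 15, 22, 29 and 60. Keep the within-arm visit means as least squares means from the same model. The baseline lesional-minus-non-lesional difference may be added as a covariate, but this is optional. State the covariance structure, which the current sentence does not give.

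The cost is wording only, with no new data or visits. The statistical price is a common covariance across arms, which the other sub-study models, as described, already assume. Make the same change in the separate sub-study SAP or, if that document already specifies the contrast, bring the protocol text into line with it.

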4.3. Randomization Criteria

Subjects will be randomized into the study provided that the subject or caregiver [parent/legal guardian/legally acceptable representative] has signed an informed consent (or assent, if applicable) document to participate in the study, and the subject has undergone all screening procedures, and satisfies all inclusion and exclusion criteria for participation in the study at the Baseline visit. A centralized computer-generated randomization schedule will be used to assign subjects to the treatment groups.

Subjects will be assigned to one of two cohorts prior to randomization. Subjects will be enrolled into Cohort 1 if eligible to receive TCS therapy; randomization will be 1:1:2 to crisaborole ointment, 2%, the matching vehicle ointment for crisaborole, or hydrocortisone butyrate cream, 0.1%, respectively. Subjects will be enrolled into Cohort 2 if ineligible to receive TCS therapy and eligible to receive pimecrolimus cream, 1%; randomization will be 1:1:2 to crisaborole ointment, 2%, the matching vehicle ointment for crisaborole, or pimecrolimus cream, 1%, respectively.

Subjects will be assigned a subject identification number in the order of their screening for the study. The identifying number will be retained throughout the study.

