Technical detail and set-up of the OCT measurements, TEWL, and the tape-strip procedure will be provided to participating centers in Laboratory Manuals. All sub-study evaluations will be completed after and in addition to main study procedures completed at those clinic visits. Both the operator and the accessor of images will be blinded. OCT measurements will be obtained first, followed by TEWL (if applicable) at OCT AD lesional and non-lesional target skin sites. Tape-strips for biomarkers will be conducted after OCT and TEWL measurements at the tape-strips target skin site.

Both the OCT AD lesional target skin site and the non-lesional target skin site will be imaged by OCT in triplicate on Baseline/Day 1, Day 8, Day 15, Day 22, Day 29, and Day 60. The operator should be consistent across all imaging taken for each individual subject. An Imaging partner will be responsible for standardizing the OCT image acquisition, training the centers on the imaging protocol, ensuring equipment and image quality assurance and quality control. Image analysis will be conducted by a central reader(s) who will be blinded. Detailed procedures for obtaining and processing the OCT image, conducting image quality assurance/quality control and endpoint analyses will be described in study specific documents and provided as appropriate to the study centers.

TEWL will be measured at both the OCT AD lesional target skin site and the non-lesional target skin site (not at the tape-strips lesional target skin site) on Baseline/Day 1, Day 8, Day 15, Day 22, Day 29, and Day 60 at selected sub-study centers. The operator should be consistent across all measurements taken for each individual subject.

Tape-strips for biomarker collection will be completed at the non-lesional target skin site on Baseline/Day 1 only. Tape-strips for biomarker collection will be completed at the tape-strips lesional target skin site on Baseline/Day 1, Day 15, and Day 29. The operator should be consistent across all tape-strip collections for each individual subject. The operator will be blinded. A tape strips biomarker partner will be responsible for standardizing the collection and analysis of biomarkers. Detailed procedures for biomarker collection, processing and analysis will be described in a separate document and provided to the study centers.

Prior and concomitant treatments

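### As written, the tape-strip biomarker model compares arms on change without adjusting for baseline: unbiased, but generally less precise than using Day 1 expression as a covariate

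*Protocol*

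**What the plan says.** All of this is in Protocol Appendix 4 unless noted.

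- **Endpoint** (section 2, secondary): "Change from Baseline/Day 1 in skin biomarkers of AD at Day 15 and Day 29".
- **Sampling** (section 6): "Tape-strips for biomarker collection will be completed at the tape-strips lesional target skin site on Baseline/Day 1, Day 15, and Day 29". The non-lesional site is stripped on Day 1 only, so change can be estimated only at the lesional site. Target sites are left untreated on visit days until the procedures are done, so the Day 1 strips are pre-treatment.
- **Model** (section 7): the response is log2 expression at each visit, not change from Day 1. The form given for it is a "linear mixed effect model with visit, treatment, visit by treatment interaction as fixed effects and a random effect for each subject". The visits that enter the model are not listed.
- **Comparisons** (section 7): "Means of each group will be estimated using least squares means and comparisons of interest will be tested using contrast". The contrasts are not listed either.
- **Neighbouring models** (section 7): change in epidermal thickness is modelled with "treatment by visit interaction as factors and baseline value as a covariate, separately for OCT AD lesional target skin site" and likewise for the non-lesional site. For percentage change in TEWL, the section states that baseline is not a covariate. For the biomarkers it is silent.
- **Size and aim** (section 7): "Approximately 60 subjects (15, 15, 30 in vehicle, crisaborole, hydrocortisone groups respectively) will participate this sub-study from Cohort 1". The sub-study is called a pilot, without a power calculation, to be read through estimation.
- **Further detail**: SAP section 2.2 defers the sub-study analysis to a separate SAP, which is not available here.

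**The concern.** The response is expression at each visit, yet the endpoint is change from Day 1. The model can deliver that endpoint only if Day 1 is one of its visits, and the interaction then gives every arm a free Day 1 mean. Randomised arms share the same expected baseline, so estimating a separate one for each spends information on a difference whose expectation is zero. The subject effect does not repair this: with complete data the contrast of change is the difference in raw mean changes, which fixes the slope on baseline at 1. Any chance imbalance at Day 1 then enters the estimate at that slope, whether or not it suits the data.

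What is at stake is the width of the intervals in a sub-study with 15 subjects in each of two arms, where estimation is the stated purpose.

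**Working it through.** **1. The plan's own figure.** Cohort 1 allocation (Protocol section 4.3): "randomization will be 1:1:2 to crisaborole ointment, 2%, the matching vehicle ointment for crisaborole, or hydrocortisone butyrate cream, 0.1%, respectively". With 60 subjects, 60 × 1/4, 60 × 1/4 and 60 × 2/4 give 15, 15 and 30, as stated. The documents give no SD, correlation or precision for the biomarkers, so these are assumed below and shown as ranges.

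**2. Formulas.** Let s be the baseline SD, ks the Day 29 SD, ρ the correlation between them, and m = 1/n₁ + 1/n₂. With complete data, before the cost of estimating a slope:

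- planned contrast of change: variance = s²(1 + k² − 2ρk)m
- baseline as covariate: variance = s²k²(1 − ρ²)m
- planned minus adjusted = s²(1 − ρk)²m, which is never negative and is zero only when ρk = 1.

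**3. Equal SDs (k = 1).** The variances become 2s²(1 − ρ)m and s²(1 − ρ²)m, so the SE ratio, adjusted to planned, is √((1 + ρ)/2). Standard errors in SD units:

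| ρ | 15 vs 15, planned → adjusted | 15 vs 30, planned → adjusted | SE reduction |
|---|---|---|---|
| 0.3 | 0.432 → 0.348 | 0.374 → 0.302 | 19% |
| 0.5 | 0.365 → 0.316 | 0.316 → 0.274 | 13% |
| 0.7 | 0.283 → 0.261 | 0.245 → 0.226 | 8% |
| 0.9 | 0.163 → 0.159 | 0.141 → 0.138 | 3% |

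For example, at ρ = 0.5 with 15 vs 30, m = 0.1: √(2 × 0.5 × 0.1) = 0.316 and √(0.75 × 0.1) = 0.274.

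**4. Unequal SDs.** The SE ratio is √[k²(1 − ρ²)/(1 + k² − 2ρk)].

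- k = 1.25: at ρ = 0.3, √(1.422/1.813) = 0.886, a reduction of 11%; at 0.5, √(1.172/1.313) = 0.945, or 5.5%; at 0.7, √(0.797/0.813) = 0.990, or 1%.
- k = 1.5: √(2.048/2.350), √(1.688/1.750) and √(1.148/1.150), reductions of about 7%, 2% and 0.1%.

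As ρk approaches 1, the best slope approaches the slope of 1 that the change score already uses.

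**5. Small-sample cost of the covariate.** With 60 subjects, estimating the slope multiplies the variance by about 1 + 1/55 = 1.018. A simulation with equal SDs (15/15/30, 8,000 runs per ρ) put the planned SE above the adjusted SE by 24%, 14%, 7% and 1% at ρ = 0.3, 0.5, 0.7 and 0.9. Break-even is at 2/(1 + ρ) = 1.018, that is ρ ≈ 0.96.

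**6. A common baseline mean with only the planned subject effect.** A random intercept forces one variance and one covariance on all visits, so the implied slope is the pooled intraclass correlation. Take k = 1.5 and ρ = 0.7 between all pairs of visits. The mean variance is (1 + 2.25 + 2.25)/3 = 1.833 and the mean covariance is (1.05 + 1.05 + 1.575)/3 = 1.225, so the slope is 1.225/1.833 = 0.668. The contrast variance is proportional to 2.25 + 0.668² − 2 × 0.668 × 1.05 = 1.293, against 1 + 2.25 − 2 × 1.05 = 1.150 as planned. The SE ratio is √(1.293/1.150) = 1.06, a rise of 6%. A 6,000-run simulation gave a rise of 5.7% for this approach and 0.9% for the covariate model.

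**7. If the unlisted contrasts are arm differences at Day 29 alone**, they too are unadjusted. The SE exceeds the adjusted one by a factor 1/√(1 − ρ²): 1.15 at ρ = 0.5 and 1.40 at ρ = 0.7.

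**The case against.** The planned model is a standard one, is unbiased under randomisation, and gives within-arm change directly. With complete data its contrast does not depend on the covariance model. The gain from adjustment rests on quantities that the documents do not give, and there is reason to doubt equal SDs: the tape-strip lesion must have a local ISGA of 2 or 3 at entry (Appendix 4, sections 5 and 6), which may narrow the baseline range, while treated skin can range more widely. The section handles baseline differently by endpoint, and for TEWL it leaves it out on purpose, so the contrast with the thickness model does not by itself show an oversight. The visits and contrasts are not listed, and the sub-study SAP might specify adjustment.

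Most of this stands, and it limits the size of the point. It does not remove it. Treating Day 1 as a response visit is an inference, but no other reading of the stated model yields the stated endpoint. The excess variance (1 − ρk)² cannot be negative, so apart from the small cost of one estimated slope the covariate model does not lose.

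**Conclusion.** The point holds as a modest matter of precision. On the protocol text, between-arm comparisons of biomarker change are unadjusted for baseline. With equal SDs, adjustment would reduce the SE by about 19%, 13% and 8% at ρ = 0.3, 0.5 and 0.7; with a follow-up SD 1.25 times the baseline SD, by about 11%, 5.5% and 1%. With equal SDs the gain is negligible near ρ = 0.9. These figures assume complete data and assumed values of ρ and the SD ratio.

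A reader might infer more than the documents support:

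- **That the planned estimate is biased.** It is not: chance imbalance adds variance, and randomisation keeps its expectation at zero.
- **That power is lost.** None is planned. The section disclaims formal testing, although it then speaks of testing contrasts.
- **That every biomarker interval is materially too wide.** When ρk is close to 1, the change score is already close to optimal.
- **That a common baseline mean is interchangeable with a baseline covariate.** With only the planned random intercept it can raise the SE, by about 6% in the example above.
- **That the sponsor has no adjustment planned.** The sub-study SAP has not been seen.

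SAP section 5.1 records that the main study stopped with 40% of planned participants enrolled and became descriptive. The documents do not say what happened to the sub-study, which is to be reported separately. The point applies to any between-arm biomarker estimate that is still made.

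**What to change.** In Appendix 4, section 7, or in the sub-study SAP: for between-arm comparisons on the lesional strips, model Day 15 and Day 29 log2 expression with treatment, visit, treatment by visit and baseline log2 expression as a covariate, preferably with baseline by visit. This follows the approach that the section already takes for epidermal thickness. List the contrasts and report the Day 15 and Day 29 arm differences with 95% confidence intervals. Within-arm change can still come from the planned model.

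One alternative is to keep Day 1 as a response with a single mean across arms, but only with an unstructured covariance, not with the random intercept alone.

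The cost is a sentence of text and no new samples. The downsides are one or two degrees of freedom, a trivial loss of precision if the correlation is very high, and the exclusion from the covariate model of any subject without a Day 1 strip.
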